#### LIST OF ABBREVIATIONS AND RELEVANT DEFINITIONS

ABR form, General Assessment and Registration form, is the application form that is required for submission to the accredited Ethics Committee (In Dutch, ABR =

Algemene Beoordeling en Registratie)

AE Adverse Event

AR Adverse Reaction

**CA** Competent Authority

CCMO Central Committee on Research Involving Human Subjects; in Dutch: Centrale

**Commissie Mensgebonden Onderzoek** 

CV Curriculum Vitae

**DSMB** Data Safety Monitoring Board

**EU** European Union

**EudraCT** European drug regulatory affairs Clinical Trials

GCP Good Clinical Practice

IB Investigator's Brochure

IC Informed Consent

IMP Investigational Medicinal Product

IMPD Investigational Medicinal Product Dossier

METC Medical research ethics committee (MREC); in Dutch: medisch ethische toetsing

commissie (METC)

(S)AE (Serious) Adverse Event

SPC Summary of Product Characteristics (in Dutch: officiële productinfomatie IB1-tekst)

Sponsor The sponsor is the party that commissions the organisation or performance of the

research, for example a pharmaceutical

company, academic hospital, scientific organisation or investigator. A party that provides funding for a study but does not commission it is not regarded as the

sponsor, but referred to as a subsidising party.

SUSAR Suspected Unexpected Serious Adverse Reaction

Wbp Personal Data Protection Act (in Dutch: Wet Bescherming Persoonsgevens)
WMO Medical Research Involving Human Subjects Act (in Dutch: Wet Medisch-

wetenschappelijk Onderzoek met Mensen

#### **SUMMARY**

Rationale: For highly prevalent conditions associated with chronic itch, treatment effects are usually modest and vary strongly across patients. Expectancy mechanisms may contribute to this variability. The influence of expectations have often been studied in a placebo- or nocebo design, in which expectations are, for example, induced by verbal suggestions or a conditioning procedure. Placebo and nocebo effects can be defined as favorable and unfavorable treatment responses, unrelated to the treatment mechanism, which are induced by expectations of improvement and worsening, respectively. Placebo and nocebo effects have been investigated primarily in studies that focus on pain. Recent research of our research group showed in a validated design that expectancy mechanisms of verbal suggestion and conditioning can also induce placebo and nocebo effects on itch. However, it is not yet known whether nocebo effects can also actively be modified, e.g., by inducing a positive expectation induction, resulting in less itch. This is a scientifically and clinically highly relevant research question for the development of treatment modules to change inadequate negative expectations of patients suffering from chronic itch complaints.

**Objective:** The main objective of the study is to determine whether induced nocebo effects (negative expectancy effects) for itch can be modified by a positive expectation induction. Secondary objectives are to explore: a) the effects of expectation inductions on scratching behavior, b) the generalization of expectancy effects to other types of itch stimuli, c) the role of individual characteristics on expectancy effects, and d) the role of genetic predispositions on expectancy effects.

Study design: In healthy subjects, expectations with regard to electrically evoked itch will be induced by a conditioning with verbal suggestion procedure, in correspondence to a previous experiment conducted by the research group (25). For every stimulus, participants are asked to report the level of itch on a Visual Analogue Scale (VAS), and the scratching behavior of the participants will be recorded during the experiment. In part I, in all participants high-itch expectations will be induced (nocebo induction). More specifically, in the learning phase, short-lasting itch stimuli of medium and high intensity are repeatedly associated with certain colored cues displayed on a computer screen (e.g., two colored cues of which one cue is associated with itch stimuli of medium intensity (neutral cue), and the other with itch stimuli of high intensity (conditioned cue)). In line with the conditioning procedure, verbal suggestions for high itch will be given regarding itch stimuli associated with the conditioned cue. Subsequently, in the testing phase, expectancy effects for itch with regard to the colored cues will be tested by applying both the conditioned and neutral cues with itch stimuli of medium intensity. In part II, participants will be randomly assigned to one of three groups: the experimental group, in which lowitch expectations will be induced (group 1) (similar to the procedure described above with the exception that the conditioned cues are now associated with low itch intensity stimuli), a control group in which once more high-itch expectations will be induced similar to part I (group 2), or a control group with a neutral itch induction procedure (neutral expectation induction) (group 3). In part III, generalization of the induced expectancy effects will be tested with respect to another itch stimulus, i.e., histamine iontophoresis.

Study population: Healthy human volunteers, aged between 18 - 35 years old.

Intervention (if applicable): Not applicable.

Main study parameters/endpoints: The main study endpoint is the difference in the levels of itch (VAS scores) evoked by the electrical stimuli associated with the conditioned cues versus the neutral cues in the testing phase of part II of the experiment. It is investigated whether nocebo effects (negative expectation effects) can be modified by a positive expectation induction by conditioning and verbal suggestion (low-itch expectation induction) (group 1), resulting in lower itch VAS scores than a repeated negative expectation induction (high-itch expectation induction) (group 2), or a neutral procedure (neutral expectation induction) (group 3).

Nature and extent of the burden and risks associated with participation, benefit and group relatedness: Participants will complete a series of validated questionnaires at home to assess relevant individual characteristics, for approximately half an hour. Participants will then visit the department of Health-, Medical & Neuropsychology at the Leiden University once for approximately 5,5 hours. Sensations of itch will be induced using frequently applied, validated stimuli of short duration which are not burdensome (e.g., [1-4], 25). DNA is collected by asking participants to spit in a special tube. No risks are involved with participation in this study, only an investment of time.

#### 1. INTRODUCTION AND RATIONALE

For highly prevalent conditions associated with chronic itch, treatment effects are usually modest and vary strongly between patients [5,6]. This treatment variability may partly be determined by patients' expectations regarding the treatment. A validated paradigm to experimentally study the influence of expectations is a placebo design, in which expectations are frequently induced by verbal suggestion or a conditioning procedure [7-10]. Placebo effects can be defined as favorable treatment responses, unrelated to the treatment mechanism, which are induced by expectations of improvement. Nocebo effects on the other hand, are unfavorable treatment responses, unrelated to the treatment mechanism, which are induced by expectations of worsening [9-11]. Placebo and nocebo effects have especially been investigated in studies that focus on pain. However, also with regard to itch, expectations seem to play an important role. There is some indirect evidence showing that patients with atopic dermatitis react differently to histamine when given verbal suggestions for exaggerated skin reactions and itch [12]. Furthermore, our research group showed experimentally that nocebo responses, and probably also placebo responses, can be induced on itch by verbal suggestions [3]. Moreover, results of our previous experiment for the first time indicated that the combination of conditioning with verbal suggestion is most effective to induce significant placebo and nocebo effects on itch [25]. However, at this point, it is still unknown whether nocebo effects (negative expectation effects) can actively be modified. This is an important research topic since nocebo effects can unfavorably affect clinical outcomes, can lead to a heightened report of side effects, and can negatively affect patients' daily health [9].

In addition to our main research objective, investigating the modifiability of the nocebo effect on itch, we also aim to provide insights in some secondary research topics. First, scratching behavior will additionally be measured, since itch is defined as an unpleasant sensation that can induce the urge to scratch [6,13]. Expectancy effects on itch VAS scores will be compared to the effects on scratching behavior. Furthermore, the possible extending of expectancy effects to other itch stimuli will be investigated, by assessing the generalization of expectancy effects regarding histamine iontophoresis. Additionally, individual characteristics may partly determine the magnitude of induced expectancy effects. For example, subjects scoring low on optimism are more likely to follow nocebo expectations [14]. Moreover, in our previous study on itch it was also found that individual characteristics (more negative affect, less extraversion, more neuroticism and less hope) were related to outcome expectancies, particularly with the nocebo effect [25]. Genotype is another factor that might affect individual differences in expectation responding. One relevant gene variant is the serotonin transporter length polymorphhic region (5-HTTLPR), for which two alleles have been identified, the short (s) and the long (I) allele. There is accumulating evidence that the 5-HTTLPR-s allele is associated with increased Pavlovian conditioning (e.g. [15,16]) and increased sensitivity to phrased descriptions of choice options in a decision making task [17]. Therefore, we hypothesize that 5-HTTLPR s-allele carriers may show increased responsivity to verbal suggestion and conditioning. Similarly, other potentially relevant genetic variants will be tested for their involvement in these phenotypes, when possible relationships would emerge from literature.

The present research project aims to enhance the understanding of psychophysiological mechanisms of conditioning and verbal suggestion with regard to expectancy effects on itch. For the first time, the modifiability of negative expectancy effects will be examined systematically. Therefore, first negative expectations for itch will be induced as a starting point, which will subsequently be attempted to be reduced by a positive expectation induction. These effects will be compared with two control groups in which either once more negative expectations will be induced, or a neutral procedure will be applied. In addition, mechanisms of expectation responding are further explored with regard to the effects on scratching behavior; the generalization to other itch stimuli; and the influence of individual characteristics and genetic predispositions on individual expectation responding. The results of this study will enhance our understanding of the mechanisms underlying expectancy effects on itch and can provide insight into whether negative expectancy effects can be modified. These results may eventually help to develop therapeutic interventions by reducing inadequate negative expectations in patients suffering from chronic itch conditions. The results of this study can also be relevant to all kinds of physical symptoms and conditions other than itch, in which expectancy effects may play a role.

#### 2. OBJECTIVES

## **Primary objective:**

The primary objective of the study is to determine whether induced negative expectation effects for itch can be modified. It is hypothesized that levels of itch (VAS) will be reduced after a low-itch expectation induction, in comparison to the control procedures in which high-itch expectations or neutral expectations will be induced.

## Secondary objectives:

Secondary goals are to explore:

- a) the itch related expectancy effects on scratching behavior
- b) the itch related expectancy effects regarding itch evoked by histamine iotophoresis
- c) the role of individual characteristics (e.g., optimism) on (the modifiability of) expectancy effects
- d) the role of 5-HTTLPR genotype and other genetic variants on (the modifiability of) expectancy effects

#### 3. STUDY DESIGN

Participants will complete online validated questionnaires at home which will take about 30 minutes, and will visit the department of Health, Medical & Neuropsychology of the Leiden University once, for approximately 5,5 hours. The experiment will take place in a research lab of the department.

The experiment consists of three parts (see Fig. 1 for an overview of the components of the study). In part I and II, expectations with regard to electrically evoked itch will be induced by conditioning with verbal suggestion. Individual itch thresholds are used for determining the intensity of the itch stimuli for the conditioning procedure. In part I of the experiment, all participants will be subjected to a high-itch expectation induction, in order to attain negative expectations with regard to itch as a starting point. In part II of the experiment, participants are assigned to either the experimental group, in which low-itch expectations will be induced (group 1), or one of the control groups in which either once more high-itch expectations will be induced (group 2), or neutral expectations (group 3). Participants will be asked to report their level of itch for every stimulus on a Visual Analogue Scale (VAS), and scratching behavior of the participants will be recorded during the experiment. In part III, histamine iontophoresis will be applied (with the conditioned colored cue displayed on the computer screen) and in addition participants are asked to spit in a special tube to collect saliva for DNA isolation.

### **Expectation induction procedures**

### Part I

#### High-itch expectation induction (all participants)

High-itch expectations will be induced in all participants regarding electrical stimuli by conditioning with verbal suggestion. A conditioning procedure will be applied in which a specific colored cue displayed on a computer screen is repeatedly associated with an increased intensity itch stimulus (conditioned cue). In line with the conditioning procedure, verbal suggestions for high itch will be given regarding itch stimuli associated with the conditioned cue.

#### Part II

#### Group 1: Low-itch expectation induction

Participants in this group will receive a low-itch expectation induction regarding electrical stimuli by conditioning with verbal suggestion. A conditioning procedure will be applied in which the same specific colored cue as described above displayed on a computer screen (conditioned cue) is repeatedly associated with a decreased intensity of the itch stimulus. In line with the conditioning procedure, verbal suggestions for low itch will be given regarding the itch stimuli.

[figure not shown]
### Group 2: High-itch expectation induction

Participants in this group will receive the same high-itch expectation induction as in part I, described above in part I.

## Group 3: Neutral expectation induction

Participants in this group will not receive a conditioning procedure or verbal suggestions. The two different colored cues will be shown with randomly applied itch stimuli and participants are merely told that the colored cues will indicate the start of a new stimulus.

Fig 1. Overview of the study

#### 4. STUDY POPULATION

## 4.1 Population (base)

Healthy participants aged 18 – 35 years will be included in the study. Participants will be recruited via different approaches.

#### 4.2 Inclusion criteria

Healthy human volunteers, 18 - 35 year old, fluent in Dutch language.

#### 4.3 Exclusion criteria

Severe morbidity (e.g., multiple sclerosis, diabetes mellitus, heart or lung diseases), psychiatric disorders (e.g., depression), use of pacemaker, color-blindness, diagnose of histamine hypersensitivity, and chronic itch or pain complaints.

### 4.4 Sample size calculation

The required sample size was calculated, in agreement with a statistician ([name], Radboudumc), based on our previous study with a comparable design [25]. Such as in the present study, in our previous study a comparison was made between a positive expectation induction by conditioning and verbal suggestion and a control group. In this study an average placebo effect of 0.86 (SD = 0.59) and 0.32 (SD = 0.79) was found in the *conditioning with verbal suggestion group* and the *control group*, respectively (effect size of d = 0.78). Based on these means and standard deviations, sample size calculations were done using G\*power 3.1. We simplified the analyses of the main hypotheses, Univariate analyses of variance (ANOVA's) with Dunnett contrasts, into two two-tailed independent samples t-tests (i.e., comparing the positive expectation induction group with the negative expectation induction group and the neutral expectation induction group separately) using a Bonferroni correction. For these t-tests, the means and standard deviations of the most conservative comparison in the present study were used, i.e., of the positive expectation induction with the neutral expectation induction. With an effect size of d = 0.78, an alpha of 0.025 and a desired power of 0.80, this resulted in an estimated total sample size of 33 participants per group.

## **5. TREATMENT OF SUBJECTS**

< This chapter is only applicable for intervention studies>

## 5.1 Investigational product/treatment

Not applicable

## 5.2 Use of co-intervention (if applicable)

Not applicable.

## 5.3 Escape medication (if applicable)

Not applicable.

Version number:2, date: 28-04-2014

## 6. INVESTIGATIONAL PRODUCT

<This chapter is applicable for research with any product; medicinal product, food product, medical device or other >

Not applicable.

Version number:2, date: 28-04-2014 17 of 31

### 7. NON-INVESTIGATIONAL PRODUCT

<This chapter is applicable for any other product that is used in the study, like challenge agents or products used to asses end-points in the trial. This can be a medicinal product or a food product or a chemical compound or stable isotope or other product.

This chapter does not include co-medication or escape medication, these are already mentioned in chapter 5

For products to be used as in usual clinical practice the information can be limited to the chapters 7.1, 7.6 and 7.7 >

Not applicable.

#### 8. METHODS

## 8.1 Study parameters/endpoints

#### 8.1.1 Main study parameter/endpoint

The main study endpoint is the level of itch (VAS scores) evoked by the electrical stimuli associated with the conditioned cues in comparison to the neutral cues in the testing phase of part II of the experiment. It is investigated whether nocebo effects (negative expectation effects) can be modified by a positive expectation induction by conditioning and verbal suggestion (low-itch expectation induction) (group 1), resulting in lower itch VAS scores than a repeated negative expectation induction (high-itch expectation induction) (group 2), or neutral procedure (neutral expectation induction) (group 3).

## 8.1.2 Secondary study parameters/endpoints

The secondary study endpoints of the present experiment are: a) the scratching behavior of the participants, b) the levels of itch (VAS ratings) induced by histamine iontophoresis after displaying the conditioned cue, c) the scores on several questionnaires measuring individual characteristics related to expectancy effects, d) the 5-HTTLPR genotype and possibly also other genetic variants.

### 8.1.3 Other study parameters (if applicable)

Not applicable.

### 8.2 Randomisation, blinding and treatment allocation

After part I, in which all participants are exposed to the same procedure, in part II participants will be randomly allocated to one of three experimental groups (see section 3. Study design and Fig 1.). We will use a single blind design: Since the instructions given to the subjects differ in accordance with the group the subjects are allocated to, only subjects will be blinded for the randomization to different groups. No indications for breaking the randomization code are indicated.

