## 8.3 Study procedures

### **Expectation induction**

Expectations will be induced by conditioning and verbal suggestion procedures with regard to two specific colored cues being displayed on a computer screen. For half of the participants the first colored cue is the conditioned cue and the second colored cue is the neutral cue, and visa versa for the remaining participants. In part I of the experiment the high- itch expectation induction procedure, as described below, is applied for all participants. In part II, participants are allocated to one of the three experimental groups in which either the low-, high-, or neutral expectation induction is applied (see section 3. Study design and Fig 1.).

High-itch expectation induction

For the high-itch expectation induction, the intensity (mA) of the stimuli will be increased following the presentation of the conditioned cue (*expectation for high itch*) in comparison to the intensity of stimuli following the neutral cue, which is not adjusted (*neutral expectation*). In line, participants will be told that: "The specific colored cue will signal the activation of the third electrode that induces an increase in the intensity of the itch stimulus (*expectation for high itch*). The other cue will indicate that the third electrode is turned off and will not change the intensity of the itch stimulus (*neutral expectation*)".

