#### Neutral expectation induction

In the neutral group, participants will not receive a conditioning procedure or verbal suggestions; the different colored lights are randomly shown with previously defined random stimuli intensities and participants are merely told that a colored cue will indicate the start of a new stimulus.

Participants are asked to rate their levels of itch on a Visual Analogue Scale (VAS) ranging from 0 (no itch at all) to 10 (worst itch imaginable) after each stimulus. Additionally, participants are videotaped to record scratching behavior of the participants during the experimental sessions.

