## Somatosensory stimuli

Itch sensations are induced by two cutaneous electrodes applied on the forearm. A third and inactive electrode is placed between the two active electrodes and represents the sham treatment designed to induce expectations of stimulus alterations. Itch thresholds will be determined according to the protocol of our previous study [25], which was based on the protocol of Colloca [18,19], to apply stimuli with strengths adjusted to participant's individual sensitivity levels. This method showed good validity in our previous study on itch [25]. These threshold measures will be used to adjust the intensity (mA) of the stimuli for conditioning of expectations with regard to itch.

In addition, histamine iontophoresis, previously applied by our research group [1-3,20,21], will be applied to test possible generalization of expectancy effects to other types of itch stimuli. A 0.3% diphosphate histamine solution will be used in the present study. Each participant will undergo one histamine application at the inner side of the forearm, while the conditioned cue (group 1 and 2) or a neutral cue (group 3) will be presented on the computer screen.

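### Differing Part II instructions do not justify leaving staff unblinded while the Part II testing-phase and Part III itch ratings are collected

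*Protocol*

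**What the plan says.** Protocol section 8.2 states that "only subjects will be blinded for the randomization to different groups". The reason given is: "Since the instructions given to the subjects differ in accordance with the group the subjects are allocated to". No other reason appears.

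The same section fixes the timing: "After part I, in which all participants are exposed to the same procedure, in part II participants will be randomly allocated".

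Under section 8.1.1 the primary endpoint is the VAS itch level "evoked by the electrical stimuli associated with the conditioned cues in comparison to the neutral cues in the testing phase of part II". The Summary says that in the testing phase expectancy effects are "tested by applying both the conditioned and neutral cues with itch stimuli of medium intensity". Section 8.3 has participants rate itch from 0 to 10 after each stimulus. It also describes a single histamine application in Part III, shown with the conditioned cue in groups 1 and 2 and with a neutral cue in group 3.

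The protocol describes no safeguard for staff conduct once allocation is known: no separate experimenter, no recorded instruction and no private entry of ratings.

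**The concern.** The reason in section 8.2 is about giving an instruction, whereas the rule it supports covers everything after allocation. The instruction belongs to the Part II induction; the primary outcome is collected afterwards, in the testing phase, and the histamine rating later still. Different instructions earlier in the session do not require the person running those two stages to know the group.

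This matters more here than in most trials. The intervention is expectation, the outcome is a subjective rating, and section 10.1 gives the hypothesis a direction: lower itch in group 1 than in groups 2 and 3. If an experimenter who knows both the group and the hypothesis reacts differently to the two cues, the effect works through the same pathway as the scripted suggestion. The data could not separate the two. Blinding the participant does not close this route.

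**Working it through.** **1. Which stages the stated reason covers**

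| Stage | Group known under the protocol as written? | Is the difference in instructions a reason for unblinded staff? |
|---|---|---|
| Threshold calibration | No, it precedes allocation | Does not arise |
| Part I | No, same procedure for all, before allocation | Does not arise |
| Part II induction | Yes | Yes, if the instruction is given in person |
| Part II testing phase (primary VAS) | Yes | No |
| Part III histamine VAS | Yes | No |

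The Summary states the medium-intensity testing phase for Part I. It describes the group 1 and group 2 procedures as similar to Part I, apart from the low intensity in group 1's learning phase. It does not restate the testing phase for group 3. I assume it is the same there, since the primary comparison includes that group.

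**2. What kind of influence biases the primary endpoint**

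Write the endpoint for one participant as D = C − N, the conditioned-cue rating minus the neutral-cue rating. If the experimenter's conduct adds b_C to the first and b_N to the second, D moves by b_C − b_N.

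- If b_C = b_N, the shift in D is zero. General warmth or tone over the whole session cancels.
- If b_C ≠ b_N, D shifts. The contrast of group 1 with a control is biased by (b_C − b_N) in group 1 minus (b_C − b_N) in that control.

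Only an influence that is specific to the cue and also differs between groups biases the primary contrast. Part III has one application and one cue per participant, so there is no within-participant difference and this cancellation is not available.

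**3. The plan's own figure**

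Inputs from section 4.4: means 0.86 and 0.32, SDs 0.59 and 0.79, d = 0.78, two-sided alpha 0.025 per comparison, power 0.80.

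- Difference: 0.86 − 0.32 = 0.54.
- SD: √((0.59² + 0.79²)/2) = 0.697, so d = 0.54/0.697 = 0.7745.
- Two-sample t-test with the noncentral t: n = 32.54 for d = 0.78 and 32.98 for d = 0.7745. Both round up to 33 per group, as stated.

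Blinding does not enter this figure, which is unaffected.

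**4. A scale for the bias, not an estimate**

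The documents give no size for experimenter influence, so the shifts below are assumptions. With no true effect, 33 per group and SD 0.697:

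- Standard error of the contrast: 0.697 × √(2/33) = 0.172.
- Critical t (64 df, two-sided 0.025): about 2.30.
- Noncentrality: bias/0.172.

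| Assumed bias in the between-group contrast of D (VAS points) | Share of the planned 0.54 | Noncentrality | Chance of a significant contrast |
|---|---|---|---|
| 0 | 0% | 0 | 2.5% |
| 0.1 | 19% | 0.58 | 5.0% |
| 0.2 | 37% | 1.17 | 13.6% |
| 0.3 | 56% | 1.75 | 29.9% |

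**The case against.** The strongest reply is that single blinding is openly stated and that several features already limit the risk. Participants rate their own itch. Section 8.3 fixes the wording of the high- and low-itch suggestions. The endpoint is a within-participant difference, which removes any general effect of the experimenter. The protocol does not say that the suggestions are spoken live or that the experimenter sees the ratings. All of this stands and narrows the point. It does not supply a reason for unblinded conduct of the testing phase and Part III.

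Two stronger readings are tempting, and the protocol does not support them.

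- A reader might infer that staff know the group throughout the session, so that calibration and Part I could differ by group. Section 8.2 places allocation after Part I, and the thresholds are used to set the conditioning stimuli, so at those stages there is no group to know. The section does not say who holds the randomisation code or when it is opened. Early knowledge would require a list visible beforehand, which the document does not state.
- A reader might infer that the groups differ only in one script. The conditioning intensities in Part II and the cue in Part III also differ, so recording the instructions would not by itself keep an experimenter blind if the screen or the ratings could be seen.

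A further fair objection is that recorded delivery might change the induction. The protocol bases its procedure and its sample size on a previous experiment, and does not say how the suggestions were delivered there. Recorded instructions are therefore an option below and not a condition.

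**Conclusion.** The point holds for the period after allocation in which itch ratings are collected: the Part II testing phase and the Part III histamine rating. The reason in section 8.2 does not justify leaving staff unblinded there, and no mitigation is described.

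The size of any bias cannot be estimated from the documents. The 5%, 14% and 30% figures are correct arithmetic on assumed shifts. They show that a bias of a few tenths of a VAS point would matter against a planned difference of 0.54; they say nothing about how likely such a bias is. That it would favour group 1 is plausible given the directional hypothesis, but it is not shown. For the primary endpoint, the conclusion rests on the influence being cue-specific.

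This is an inexpensive improvement to the credibility of the primary result. It is not a flaw that invalidates the design, and the sample size needs no change.

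**What to change.** Amend section 8.2, with matching text in section 8.3, as follows.

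1. Software runs each group's cue and intensity sequence in Part II and the cue display in Part III, with the screen out of the experimenter's view.
2. Participants enter every Part II testing-phase rating and the Part III ratings themselves, unseen by the experimenter and without interaction during the rating.
3. Where acceptable to the investigators, the fixed Part I and Part II instructions are given on screen or by recording, so that the experimenter can stay blind. Treating Part I the same way keeps delivery uniform across the session.
4. If live delivery is kept, the person giving the instructions will know the group. Items 1 and 2 still apply and limit what that knowledge can influence.

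Cost: some programming, on a system that already shows the cues on a computer screen. Items 1 and 2 need no extra staff and leave the induction unchanged. Item 3 carries the one scientific downside, a possibly less persuasive suggestion. Even then, blinding is not guaranteed, because a participant's remarks could reveal the group.
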